- ^k DEXA will be conducted at 12-month intervals at all study sites where the DEXA device is available. Please refer to [Section 9.7.7](#) for additional information related to the allowed windows at Day 0 for this procedure.
- ^l Endoscopy will be conducted at all study sites where the device is available to assess for the presence of oesophageal varix/varices. Please refer to [Section 9.7.7](#) for additional information related to the allowed window at Day 0 for this specific procedure.
- ^m Ultrasound will be conducted to enhance HCC surveillance. For all on study (eg, post-Day 0) ultrasounds: Unless HCC has already been confirmed by biopsy, a second confirmatory image (eg, MRI) should be obtained to confirm suspected HCC.
- ⁿ Health Outcome Assessments: Data related to nonstudy related medical or surgical treatment procedures that the subject underwent and any medically relevant health care provider (HCP) or non-HCP related office visits that the subject attended should be collected throughout the study.
- ^o Pre-titration tolerability assessment, which include a review of AEs and a review of safety laboratory results (eg, chemistry, hematology, and coagulation), must be completed by the Investigator before any up-titration can occur as defined in [Section 7.4.1](#). Lab results obtained within 2 months prior to any up-titration may be used for assessment.
- ^p Dose Titration is based on cirrhosis status ([Section 9.7.3](#)) and Child-Pugh Score ([Section 9.7.4](#)). The initial dose titration of investigational product may occur at the Month 3 visit, or any study visit thereafter for subjects on all dosing regimens, based on tolerability and biochemical response. Subsequent dose titration(s) for subjects who are classified as Child-Pugh B or Child-Pugh C and following a modified dosing schedule may occur no earlier than 6 weeks after the previous dose titration. For complete modified dose titration criteria, refer to [Appendix A](#).
- ^q Subjects will be instructed to begin dosing on the day after the Day 0 visit (ie, on Day 1) and to take investigational product at approximately the same time of day. Subjects must be instructed to swallow the tablet whole; they must not chew, divide, or crush the tablet.
- ^r The subject should be instructed to fast overnight (at least 8 hours) prior to each visit. Fasting is required prior to all study visits (except Screening Visit 1) but water is permitted.

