7.4. Dose Titration Criteria

Dose titration may follow the scheduled dosing regimens described in [Section 7.3](#) or occur due to tolerability concerns or as a result of changes in a subject's cirrhosis status (using histology or non-histological methods as defined in [Section 9.7.3](#) and [Section 9.7.4](#)) or Child-Pugh Score.

Dose titrations may involve increases or decreases in dosing frequency or dose and are dependent on tolerability (as assessed by a review of AEs and safety laboratory results) as well as biochemical response (as assessed by reductions in ALP and/or total bilirubin). In general, down-titration will be done in response to tolerability concerns and can occur at any time while on-study. Up-titration will be done per protocol when subjects have no tolerability concerns and have not achieved an adequate reduction in ALP and/or total bilirubin to within normal limits, or as assessed by the Investigator, or following resolution of a tolerability concern that previously led to down-titration. Up-titrations may only occur to the maximum dose and frequency for each dosing regimen as defined in Section 7.3.

Scheduled Dose Titration - The first dose titration for any subject may occur no earlier than 3 months following initiation of OCA or matching placebo. Subsequent titrations in dose or dosing frequency for subjects following the Modified Dosing Regimens may occur no earlier

than 6 weeks (via an unscheduled visit or regular visit- see [Appendix A](#)) following an up-titration.

Tolerability Dose Titration - Investigators may decrease the dosing frequency or dose for any subject at any time during the study, as considered clinically appropriate (eg, tolerability; see [Section 7.4.1](#)).

Dose Titration due to Change in Cirrhosis or Child-Pugh Score - When subjects demonstrate a change in cirrhosis status (as assessed per [Section 9.7.3](#)) or Child-Pugh Score ([Section 9.7.4](#)), dosing should be reassessed and the dosing regimen modified appropriately. Changes to the dosing regimen are not mandatory and should be based on clinical judgment as well as change in cirrhosis status. Table 5 provides an overview of the possible changes in dosing regimen due to changes in cirrhosis or Child-Pugh Score. Dosing should follow the titration schedule of the new dosing regimen such that the maximum dose within that dosing regimen is ultimately attained, based on tolerability, biochemical response, and clinical judgment.

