7.4.1. Pre-Titration Tolerability Assessment Requirements

Tolerability of investigational product must be assessed prior to titrating a subject to a higher dose. A review of adverse events and safety laboratory results (eg, chemistry, hematology, and coagulation) obtained within 2 months of the up-titration visit must be performed as part of the investigational product tolerability assessment, prior to any planned up-titration in study medication (eg, Month 3, Month 6). Safety laboratory results obtained at the Month 1 visit (for titration at Month 3) or at the 1 Month Post-Titration Assessment visit (for titration prior to or at the subsequent quarterly visit) are acceptable for review purposes; however, if for any reason, laboratory results are not available at the time of the planned up-titration visit, additional laboratory samples must be obtained and reviewed, prior to up-titrating the subject to a higher dose.

To be eligible for a dose up-titration:

- Subjects should not be experiencing significant AEs that are suspected to be related to investigational product (eg, severe pruritus) or displaying other symptoms that may indicate intolerability of investigational product.
- There must be no clinically significant increase (as determined by the Investigator) in the subject's liver function tests.

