following review of the pre-titration laboratory results to assess safety and tolerability, the dosing frequency of 5 mg OCA or matching placebo should be increased to twice weekly (at least 3 days apart). Subjects who have maintained the twice weekly dosing frequency for a minimum of at least 6 weeks, and meet the dose titration criteria, should up-titrate to twice weekly dosing with 10 mg OCA or matching placebo. Subjects with at least 6 weeks of twice weekly dosing at 10 mg OCA or matching placebo, and meeting dose titration criteria, should up-titrate to the maximum allowed dose of 5 mg OCA or matching placebo once daily.

Investigators may decrease the dosing frequency (back to once or twice weekly) or dose for any subject at any time during the study, as considered clinically appropriate (eg, tolerability).

Modified Dosing Regimen for Subjects with Child-Pugh C Hepatic Impairment

Subjects with cirrhosis and classified as Child-Pugh C at Screening will follow a modified dosing schedule receiving 5 mg OCA or matching placebo once weekly as described in [Figure 2](#). After a minimum of 3 months dosing once weekly with 5 mg OCA or matching placebo, and following review of the pre-titration laboratory results to assess safety and tolerability, the dosing frequency of 5 mg OCA or matching placebo should be increased to twice weekly (at least three days apart). Subjects who have maintained the twice weekly dosing frequency for a minimum of at least 6 weeks, and meet the dose titration criteria, should up-titrate to the maximum allowed dose of 10 mg OCA or matching placebo twice weekly.

Investigators may decrease the dosing frequency (back to once weekly) or dose for any subject at any time during the study, as considered clinically appropriate (eg, tolerability).

Dose Titration due to Change in Cirrhosis or Child-Pugh Score

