Subjects on a modified dosing regimen who demonstrate a change in cirrhosis status and/or Child-Pugh Score should have their dose of investigational product modified to match their current status per the appropriate dosing regimen (see [Section 7.4](#), [Table 5](#)); however, changes to the dosing regimen are not mandatory and should be based on clinical judgment as well as changes in status. Changes in Child-Pugh Score that result from a transient, explainable change in laboratory parameters should be documented appropriately, and should not necessarily result in a change to the dosing regimen. Investigators may contact the Medical Monitor at any time to discuss potential changes to dosing.

Possible scenarios for dosing modifications include:

- Subjects who develop cirrhosis during the course of the trial with a classification of Child-Pugh B or C
- Subjects with pre-existing cirrhosis who demonstrate a change in the Child-Pugh Score from A to B or C at any point in the study
- Improvement in classification of Child-Pugh Score from C to B
- Improvement in classification of Child-Pugh Score from B to A; these subjects may be eligible to transition to the standard dosing regimen

Subjects may titrate dose and dosing frequency up or down as appropriate, within the appropriate dosing regimen. Up-titration should be done per Investigator discretion and be guided by the pre-titration tolerability assessments outlined in [Section 7.4.1](#). A 1-Month Post-Titration

Assessment must be performed any time a subject's dose or frequency is up-titrated (see [Section 7.1.2](#) and [Section 9.7.10](#)).

Unscheduled Titration Visit, Optional Visit

An unscheduled up-titration visit may be scheduled for as early as 6 weeks after the initial titration visit (or subsequent titration visit) occurs for subjects who are following the modified dosing regimen. The visit procedures required for the unscheduled titration visit are outlined below. Subjects who up titrate at an unscheduled visit will continue to follow the regular visit schedule for all other study visits.

For subjects who up titrate at an unscheduled visit the following procedures will be performed:

- Assess and record AEs.
- Review and record concomitant medications.
- Perform the pre-Titration Tolerability Assessment as outlined in [Section 7.4.1](#).
- Assess the subject's supply of investigational product to ensure an adequate amount. Access the IWRS and dispense investigational product if necessary.

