- Provide the subject with a dosing diary to document his or her dosing.
- Schedule the next visit, reiterate dosing instructions, and advise the subject:
 - NOT to take investigational product on the morning of the next visit, and
 - To bring the investigational product bottle(s); s/he will dose at the clinic (if this is in compliance with the established dosing frequency), and
 - To fast overnight (at least 8 hours) prior to the next visit. Fasting is required prior to all study visits, but water is permitted.

For subjects who up titrate at an unscheduled visit: The + 1-week window week related to the 1-Month Post-Titration visit can be extended for up to an additional 5 weeks to allow for the post-titration assessment to be performed during one of the subject's regularly scheduled study visits. If the window is extended past +1 week allowed visit window, at a minimum, a telephone safety contact should then be performed 1-month post-titration.

**APPENDIX B. ETHICAL CONDUCT ACCORDING TO THE
DECLARATION OF HELSINKI FOR COUNTRIES
PARTICIPATING OUTSIDE THE US (DECLARATION
OF HELSINKI, FORTELEZA, BRAZIL, 2013)**

11/11
11/11
11/11

11/11
11/11
11/11
11/11
11/11

11/11

11/11
11/11
11/11
11/11
11/11
11/11
11/11
11/11
11/11
11/11

11/11
11/11
11/11
11/11

11/11
11/11
11/11
11/11
11/11
11/11

11/11
11/11
11/11
11/11
11/11
11/11

11/11
11/11

11/11
11/11
11/11

11/11

11/11
11/11
11/11
11/11
11/11

11/11
11/11

11/11

11/11
11/11
11/11
11/11
11/11
11/11
11/11

11/11
11/11
11/11
11/11

11/11

11/11
11/11
11/11
11/11

11/11
11/11
11/11
11/11

11/11

11/11
11/11
11/11
11/11
11/11
11/11
11/11

11/11
11/11
11/11
11/11

Figure 1

100
 90
 80
 70
 60
 50
 40
 30
 20
 10
 0

Figure 2

100
 90
 80
 70
 60
 50
 40
 30
 20
 10
 0

100
 90
 80
 70
 60
 50
 40
 30
 20
 10
 0

100

100

100

100
 90
 80
 70
 60
 50
 40
 30
 20
 10
 0

100

100

100

100
 90
 80
 70
 60
 50
 40
 30
 20
 10
 0

100

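### A deferred post-titration visit lets Child-Pugh B subjects go from 10 mg twice weekly to 5 mg daily on liver tests drawn at 5 mg twice weekly

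*Protocol*

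**What the plan says.** Child-Pugh B subjects step from 5 mg once weekly to 5 mg twice weekly (Titration 1, from Month 3), then 10 mg twice weekly (Titration 2), then 5 mg daily (Titration 3). Titrations 2 and 3 may each follow the previous step after six weeks (Section 7.3, Table 3; Appendix A, Table 12). For Titration 3, Appendix A addresses "Subjects with at least 6 weeks of twice weekly dosing at 10 mg OCA or matching placebo, and meeting dose titration criteria".

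The safeguards are these:

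- **Look-back.** Section 7.4.1 requires a review of adverse events and safety laboratory results from within two months before an up-titration. Table 1 footnote o and Table 2 footnote n (Section 7.1.2) say: "Lab results obtained within 2 months prior to any up-titration may be used for assessment".
- **Which results count.** Section 7.4.1 says that results obtained "at the 1 Month Post-Titration Assessment visit (for titration prior to or at the subsequent quarterly visit) are acceptable for review purposes".
- **Missing results.** New samples must be drawn and reviewed "if for any reason, laboratory results are not available at the time of the planned up-titration visit".
- **Criteria.** Liver tests must show no rise that the investigator judges clinically significant (7.4.1). Titration also depends on biochemical response (7.4).
- **Post-titration visit.** In the modified regimens it falls 1 month (+1 week) after each up-titration. Appendix A repeats that a 1-Month Post-Titration "Assessment must be performed any time" dose or frequency is raised.

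After an unscheduled up-titration, Appendix A relaxes the last item: the window for the 1-month "Post-Titration visit can be extended for up to an additional 5 weeks", so that it can coincide with a regular visit, with a telephone contact as the minimum at one month. The procedures listed for the unscheduled titration visit include the 7.4.1 assessment but no blood draw of their own.

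**The concern.** On the default schedule the order looks after itself. Post-titration blood is drawn 30-37 days after a step and the next step is allowed at day 42, so results at the current dose exist before the dose rises again. The five-week extension breaks that order, because it moves the blood draw past the point at which the next step is allowed. The two-month look-back is long enough for the previous sample, taken one dose level lower, to remain usable. No sentence requires the reviewed results to postdate the preceding up-titration.

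At stake is a mandatory liver-test condition in cirrhotic subjects, which could be judged met on blood drawn before the dose whose tolerability is in question. Section 5.5.2.2 predicts 8.0-fold plasma and 1.5-fold liver exposure in Child-Pugh B relative to normal hepatic function. It also reports no evident effect on overall safety in hepatically impaired subjects.

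**Working it through.** The protocol gives no figure to reproduce; this is calendar arithmetic on its own windows.

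**Inputs.** Six weeks between steps (Table 3, Appendix A); post-titration visit at 1 month + 1 week (Table 1 footnote b); extension of 5 weeks (Appendix A); look-back of 2 months (7.4.1); Month 6 visit ±2 weeks (9.7.1).

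**Assumptions.** 1 month = 30 days; 2 months = 61 days (range 59-62); 3 months = 91 days; Month 6 = day 182. Titration 1 is made at Month 3, day 91.

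| Step | Arithmetic | Day | Weekly dose |
|---|---|---|---|
| Titration 1 | Month 3 | 91 | 2 × 5 = 10 mg |
| Blood after Titration 1 | 91 + 30 to 91 + 37 | 121-128 | 10 mg |
| Earliest Titration 2 (unscheduled) | 91 + 42 | 133 | 2 × 10 = 20 mg |
| Blood after Titration 2, default | 133 + 30 to 133 + 37 | 163-170 | 20 mg |
| Blood after Titration 2, extended limit | 133 + 37 + 35 | 205 | |
| Earliest Titration 3 | 133 + 42 | 175 | 7 × 5 = 35 mg |

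**Default order.** Blood is due by day 170, before day 175. There is no gap.

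**With the extension.** No sample at 20 mg per week need exist on day 175. The last one is then 175 − 128 = 47 to 175 − 121 = 54 days old, inside the look-back even at 59 days.

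**How wide the path is.** The samples stay usable until 121 + 61 = 182 or 128 + 61 = 189 (range 180-183 or 187-190). Titration 2 must therefore fall by 182 − 42 = day 140 or 189 − 42 = day 147, and Titration 3 falls on days 175-189.

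**The Month 6 visit.** Its window is 182 ± 14 = days 168-196, which contains every one of those Titration 3 dates. It includes chemistry, hematology and coagulation (9.7.11), always after Titration 2. So the gap opens in two ways:

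1. The site up-titrates at an unscheduled visit without yet holding Month 6. With Titration 3 on day 175, the first sample after Titration 2 comes 182 − 175 = 7 days later at the nominal Month 6, and at most 196 − 175 = 21 days later.
2. The site up-titrates at Month 6 with that day's results pending. At day 182 the earlier results are 182 − 128 = 54 to 182 − 121 = 61 days old, and Month 6 is the next quarterly visit that 7.4.1 refers to.

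If Month 6 is held on day 168 and its results are reviewed, there is no gap.

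**A variant that does not depend on Month 6.** If Titration 1 is made at a Month 6 visit held 14 days early (day 168), then Titration 2 = 210, Titration 3 = 252, and the Month 9 window opens at 273 − 14 = 259, which is 7 days later. With Titration 1 on day 174 (8 days early), Titration 3 = 258, 1 day before the window opens.

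**Child-Pugh C.** Subjects starting on that regimen are not exposed. Their last step is Titration 2, and it follows a post-titration visit to which the extension does not apply.

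**The case against.** The strongest reply is that this is a silence rather than an error, and that the protocol read as a whole already points to current-dose results. Response to 10 mg twice weekly cannot sensibly be judged on blood drawn before that dose. Samples must be obtained when results are unavailable for any reason, which arguably covers results pending at Month 6. The unscheduled visit incorporates the 7.4.1 assessment, and Section 9.7.19 allows extra tests at unscheduled visits. The extension exists to merge the assessment into a quarterly visit that has its own blood draw, so making Titration 3 before that visit defeats its purpose. The early-visit variant needs several coincidences and opens only a 1-7 day gap.

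Part of this stands. The path is narrow, a careful investigator would probably wait, and up-titration is discretionary. Adverse-event review, the telephone contact, free down-titration, quarterly blood tests and the interruption rules of Section 8.4.1.2 all remain.

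It does not close the gap. The additional-sample clause is triggered by unavailable results, and earlier results inside two months are available. The biochemical-response criterion sets no sampling date. Section 7.4.1 expressly accepts earlier post-titration results at the next quarterly visit. Deferring the assessment to Month 6 and titrating there is an ordinary use of the extension, since Table 1 lists Month 6 as a modified-dosing titration visit.

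**Conclusion.** The concern holds, as a minor point of patient safety. For a Child-Pugh B subject with an unscheduled Titration 2 on days 133-147 (133-140 if the earlier blood was drawn on day 121), the protocol as written does not prevent a move from 20 to 35 mg per week on blood drawn at 10 mg per week. On day 175 that blood is 47-54 days old. This rests on the month lengths stated above, on Titration 1 at day 91, and on the site either titrating before Month 6 or not waiting for its results; the early-visit variant does not need that last condition. The protocol gives no number of Child-Pugh B subjects, so the number exposed cannot be estimated. The efficacy conclusions are not affected.

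**What to change.** For the modified regimens, state in Section 7.4.1 and Appendix A that:

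- no further up-titration may be made until safety laboratory results drawn after the preceding up-titration have been reviewed; and
- the five-week extension may not be used if another up-titration is to be made before that review.

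Align Table 1 footnote o and Table 2 footnote n. Confining the rule to the modified regimens leaves the re-challenge exemption in Section 7.3 untouched.

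The cost is protocol wording and the timing of a sample that is already required. It would be drawn on days 163-170 instead of day 182, which is 182 − 170 = 12 to 182 − 163 = 19 days earlier. Section 9.7.10 already allows off-site collection with a central laboratory kit. A Month 6 visit held on days 168-170 serves both purposes with no extra visit. Otherwise Titration 3 waits for the Month 6 results.

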APPENDIX C. REFERENCE LABORATORY VALUES FROM CENTRAL LABORATORIES

Covance Central Laboratories (Indianapolis, Indiana, US [for North America and Latin America regions]; Geneva, Switzerland [for Europe]; and Singapore [for Asia-Pacific region]) will serve as the central labs for analysis or specimen management for the analytes listed in the [Table 11](#) of Protocol 747-302 Version 4. The following in text table provides the Covance Laboratory reference ranges for the pertinent liver biochemistries analyzed by Covance. These reference ranges are sex and/or age specific, and can change during the course of the clinical trial; therefore, investigative sites should always refer to the reference ranges available on the Covance issued laboratory reports.

		Covance Indianapolis		Covance Geneva and Covance Singapore	
Analyte	Sex	Age ^a	Reference Range	Age ^a	Reference Range
Albumin	Both	18Y – 69Y	SI Units: 33-49 g/L Conventional Units: 3.3-4.9 g/dL	18Y – 69Y	33-49 g/L
		69Y-80Y	SI Units: 33-46 g/L Conventional Units: 3.3-4.6 g/dL	69Y-80Y	33-46 g/L
		80Y-150Y	SI Units: 30-46 g/L Conventional Units: 3.0-4.6 g/dL	80Y-150Y	30-46 g/L
ALP	Female	18Y - 50Y	31-106 U/L	18Y - 50Y	31-106 U/L
		50Y - 60Y	35-123 U/L	50Y - 60Y	35-123 U/L
		60Y - 70Y	35-123 U/L	60Y - 70Y	35-123 U/L
		70Y - 80Y	35-123 U/L	70Y - 80Y	35-123 U/L
		80Y - 90Y	35-135 U/L	80Y - 90Y	35-135 U/L
		90Y – 150Y	35-140 U/L	90Y – 150Y	35-140 U/L
ALP	Male	18Y - 50Y	31-129 U/L	18Y - 50Y	31-129 U/L
		50Y - 60Y	35-131 U/L	50Y - 60Y	35-131 U/L
		60Y - 70Y	35-125 U/L	60Y - 70Y	35-125 U/L

		Covance Indianapolis		Covance Geneva and Covance Singapore	
Analyte	Sex	Age ^a	Reference Range	Age ^a	Reference Range
		70Y - 80Y	35-130 U/L	70Y - 80Y	35-130 U/L
		80Y - 90Y	35-125 U/L	80Y - 90Y	35-125 U/L
		90Y - 150Y	35-125 U/L	90Y - 150Y	35-125 U/L
ALT	Female	18Y - 69Y	6-34 U/L	18Y - 69Y	6-34 U/L
		69Y - 150Y	6-32 U/L	69Y - 150Y	6-32 U/L
ALT	Male	18Y - 69Y	6-43 U/L	18Y - 69Y	6-43 U/L
		69Y - 150Y	6-35 U/L	69Y - 150Y	6-35 U/L
AST	Female	18Y - 59Y	9-34 U/L	18Y - 59Y	9-34 U/L
		59Y - 150Y	9-34 U/L	59Y - 150Y	9-34 U/L
AST	Male	18Y - 59Y	11-36 U/L	18Y - 59Y	11-36 U/L
		59Y - 150Y	11-36 U/L	59Y - 150Y	11-36 U/L
Direct Bilirubin	Both	18Y - 150Y	SI Units: 2-7 umol/L Conventional Units: 0.1-0.4 mg/dL	18Y - 150Y	2-7 umol/L
Indirect Bilirubin	Both	0Y - 150Y	SI Units: 0-21 umol/L Conventional Units: 0.0-1.2 mg/dL	0Y - 150Y	0-21 umol/L
Total Bilirubin	Both	18Y - 150Y	SI Units: 3-21 umol/L Conventional Units: 0.2-1.2 mg/dL	18Y - 150Y	3-21 umol/L

ALP = alkaline phosphatase; ALT = alanine aminotransferase; AST = aspartate aminotransferase; Y = years; SI=International System of Units

^a The unstated word “to” is implied by the “dash” appearing in age specific reference ranges. A range such as “0-59 years” and “59-150 years” means: “0 up to but not including 59 years” and “59 up to but not including 150 years”.

Source: Covance Laboratory Services Manual Version 5.0.0. Dates vary by region: 10 Nov 2016 (North America), 22 Nov 2016 (Europe and Singapore)

